3.2 Background

3.2.1 Disease

Systemic lupus erythematosus is a multisystem autoimmune disease of unknown cause with diverse clinical manifestations that disproportionately affects minorities (eg, in the United States, blacks and Hispanics) and women of childbearing potential

(Rhaman and Isenberg, 2008; Kotzin, 1996). In the United States (US), moderate to severe SLE is estimated to affect one-third of the more than the 250 000 patients diagnosed with lupus. The progression of Systemic Lupus Erythematosus (SLE) may vary from mild episodes to severe, even fatal outcomes with symptoms varying widely in individuals over time and characterized by periods of remission and flare. Systemic lupus erythematosus can affect the skin (rash), musculoskeletal system (arthritis, bone tissue death), nervous system (seizures, psychosis), lungs (pleuritis, pneumonitis), and the blood (venous or arterial clots, anemia). In addition, approximately 65% of patients will develop lupus nephritis, which is an inflammation of the kidney that can range from mild glomerulonephritis to severe diffuse proliferative glomerulonephritis (Adams et al, 2006).

Currently, corticosteroids, immunosuppressants, and cytotoxic agents are frequently used to control active disease, but significant need exists for more effective therapies with fewer short- and long-term toxicities. Although the clinical heterogeneity of SLE presents challenges in the diagnosis, antibodies to nuclear components represent almost a prerequisite for the disease. The presence of class-switched immunoglobulin G (IgG) autoantibodies implicate immune dysregulation as a driving force for disease pathogenesis, with T cells appearing to play a role in the development of autoantibody production by B cells.

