10.3.2.3.3 Laboratory Test Results

The analyses of safety laboratory endpoints will include summary statistics at selected time points by treatment group. Shifts in grades of safety laboratory values between the baseline and the worst on-study value will be tabulated.

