Appendix 2. Clinical Laboratory Tests

The tests detailed in [Table 12-1](#) will be performed by the central laboratory and/or by the local laboratory.

Protocol-specific requirements for inclusion or exclusion of subjects are detailed in [Sections 6.1 to 6.2](#) of the protocol.

Additional tests may be performed at any time during the study as determined necessary by the investigator or required by local regulations.

Table 12-1. Analyte Listing

Central Laboratory			
Chemistry	Urinalysis	Hematology	Other Labs
Sodium	Specific gravity	Red blood cells	Central Laboratory:
Potassium	pH	Antinuclear antibody	Quantiferon ^b
Chloride	Blood	Hemoglobin	Hepatitis B surface
Bicarbonate	Protein (reflex urine	Hematocrit	Antigen
Total protein	protein to creatinine	MCV	Hepatitis B core
Albumin	ratio if +1)	MCH	antibody
Calcium	Glucose	MCHC	Hepatitis C virus
Magnesium	Ketones	RDW	antibody
Phosphorus	Urobilinogen	Reticulocytes	HIV
Glucose	Bilirubin	Platelets	FSH ^c
BUN or Urea	Microscopic (reflex	White blood cells	Serum pregnancy ^d
Creatinine ^a	testing if abnormal)	WBC Differential	Anti-dsDNA
Total bilirubin		• Total neutrophils or	C3 and C4 complement
Direct bilirubin		segmented	Lymphocyte subsets
ALP		neutrophils	PBMC
AST (SGOT)		• Bands	AMG 592 PK
ALT (SGPT)		• Eosinophils	Anti-AMG 592
		• Basophils	antibodies
		• Lymphocytes	Biomarker development
		• Monocytes	Pharmacogenetics
			sample
			SLE drug levels
			Urine drug/alcohol
			screen
			Local Laboratory:
			Urine Pregnancy
			PPD

ALT = alanine aminotransferase; Anti-dsDNA = anti-double stranded deoxyribonucleic acid; AST = aspartate aminotransferase; BUN = blood urea nitrogen; HIV = human immunodeficiency virus; MCH = mean corpuscular hemoglobin; MCHC = mean corpuscular hemoglobin concentration; MCV = mean corpuscular volume; RDW = red cell distribution width; PBMC = peripheral blood mononuclear cell; SGOT = serum glutamic-oxaloacetic transaminase; SGPT = serum glutamic-pyruvic transaminase; WBC = white blood cell count; MDRD = Modification of Diet in Renal Disease; PK = pharmacokinetics; FSH = Follicle stimulating hormone; PPD = purified protein derivative

^a Glomerular filtration rate will be calculated by MDRD formula

^b Quantiferon testing can be done locally or by the central laboratory

^c Can be done as a part of the clinical chemistry

^d Only at screening

Approved

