
Any abnormal laboratory test results (hematology, clinical chemistry, or urinalysis) or other safety assessments (eg, electrocardiogram [ECG], radiological scans, vital signs measurements), including those that worsen from baseline, that are considered clinically significant in the medical and scientific judgment of the investigator (ie, not related to progression of underlying disease).
 
Exacerbation of a chronic or intermittent pre-existing condition including either an increase in frequency and/or intensity of the condition.
 
New conditions detected or diagnosed after study treatment administration even though it may have been present before the start of the study.
 
Signs, symptoms, or the clinical sequelae of a suspected drug-drug interaction.
 
Signs, symptoms, or the clinical sequelae of a suspected overdose of either study treatment or a concomitant medication. Overdose per se will not be reported as an adverse event/serious adverse event unless it is an intentional overdose taken with possible suicidal/self-harming intent. Such overdoses are to be reported regardless of sequelae.
 
“Lack of efficacy” or “failure of expected pharmacological action” per se will not be reported as an adverse event or serious adverse event. Such instances will be captured in the efficacy assessments. However, the signs, symptoms, and/or clinical sequelae resulting from lack of efficacy will be reported as adverse event or serious adverse event if they fulfill the definition of an adverse event or serious adverse event.

Approved

Events NOT Meeting the Adverse Event Definition

Medical or surgical procedure (eg, endoscopy, appendectomy): the condition that leads to the procedure is the adverse event.

Situations in which an untoward medical occurrence did not occur (social and/or convenience admission to a hospital).

Anticipated day-to-day fluctuations of pre-existing disease(s) or condition(s) present or detected at the start of the study that do not worsen.

Definition of Serious Adverse Event

A Serious Adverse Event is defined as any untoward medical occurrence that meets at least 1 of the following serious criteria:

Results in death (fatal)

Immediately life-threatening

The term "life-threatening" in the definition of "serious" refers to an event in which the subject was at risk of death at the time of the event. It does not refer to an event, which hypothetically might have caused death, if it were more severe.

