**2. Objectives, Endpoints and Hypotheses**

**2.1 Objectives and Endpoints/Estimands**

Objectives	Endpoints
Primary	

To evaluate the safety and tolerability of subcutaneous (SC) dose administrations of AMG 592 in subjects with systemic lupus erythematosus (SLE)

	

Treatment-emergent adverse events

Clinically significant changes in physical examinations, vital signs, and laboratory safety tests

Secondary	

To characterize the pharmacokinetic (PK) profile following treatment with AMG 592

	

AMG 592 serum concentration and PK parameters including, but not limited to, maximum observed concentration (Cmax), the time of maximum observed concentration (Tmax), and area under the concentration-time curve over a dosing interval (AUCtau) after the first and last doses

To evaluate anti-AMG 592 antibody formation

	

Incidence of anti-AMG 592 antibodies

Cross-reactivity of anti-AMG 592 antibodies with human interleukin-2 (IL-2)

Incidence of anti-AMG 592 and anti-IL 2 neutralizing antibodies

Exploratory	

To explore the effect of treatment with AMG 592 on measures of inflammation at various time points

	

Change from baseline in anti-double stranded DNA (anti-dsDNA), and C3 and C4 complements at all time points collected

To explore the effect of treatment with AMG 592 on measures of disease activity at various time points

	

SLEDAI-2K score and change from baseline at all time points collected

To evaluate the immunological effects of AMG 592

	

Fold changes from baseline of Treg, Tcon, and NK absolute cell counts (cells/<math>\mu</math>L) after AMG 592 administration

Changes in Treg/Tcon ratio after AMG 592 administration

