#### **9.6.3         Laboratory Test Results**

**The laboratory analytes listed below in the [Table 9-1](#) will be analyzed.** Unscheduled assessments ([Appendix B](#)) will be incorporated in the laboratory analyses where possible.

**For chemistry and hematology lab analytes,** the analyses of safety laboratory endpoints will include summary statistics of baseline, post-baseline values at all time points, change from baseline to post-baseline values at all time points, post-baseline maximum/minimum and change from baseline to post-baseline maximum/minimum by treatment group. Shifts in grades of safety laboratory values between the baseline and the worst on-study value will be tabulated **based on CTCAE version 4.03.** **Subject incidence of worst post-baseline level of eosinophils counts by the laboratory normal range will be tabulated by treatment group.**

**The urine protein analyte in the urinalysis will be graded in the following manner: Negative, Trace, 1+, 2+, 3+, 4+. The number and percent of subjects in these categories at all time points will be presented.**

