#### **10.            Changes From Protocol-specified Analyses**

There are no changes to the protocol-specified analyses.

---

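### SAP 9.6.3 plans no laboratory output for urine blood, microscopy or protein/creatinine ratio, and its by-visit counts of urine protein cannot separate new from pre-existing proteinuria

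*SAP*

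**What the plan says.** SAP 2.1 puts the following in the primary endpoint: "Clinically significant changes in physical examinations, vital signs, and laboratory safety tests". SAP 9.6.1 includes laboratory measures in the primary safety analysis.

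The urinalysis column of protocol Appendix 2, Table 12-1 includes blood, protein and microscopy. A positive dipstick protein (+1) triggers a protein/creatinine ratio. Microscopy is also conditional: its row is printed as "Microscopic (reflex" and continues with the condition that the result is abnormal.

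SAP 9.6.3 sets the scope of the laboratory analysis: "The laboratory analytes listed below in the" table numbered 9-1 will be analysed. Under urinalysis, that table has one entry, urine protein. A separate paragraph describes its analysis: "The urine protein analyte in the urinalysis will be graded in the following manner: Negative, Trace, 1+, 2+, 3+, 4"+. The output is the number and percentage of subjects in each category at each time point.

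The summaries of change from baseline, the post-baseline maximum and minimum, and the CTCAE grade shifts are in a different paragraph, which opens by naming chemistry and hematology. The current 9.6.3 specifies no laboratory listing.

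Protocol 10.3.2.3.3 speaks of safety laboratory values in general: "Shifts in grades of safety laboratory values between the baseline and the worst on-study value will be tabulated".

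**The concern.** The protocol describes renal involvement as part of the disease (section 3.2.1: "approximately 65% of patients will develop lupus nephritis"), and the study drug acts on the immune system. Urine blood, sediment and protein are therefore results a reader of the safety report would expect to find. As planned, a subject who develops hematuria on AMG 592 appears in no laboratory table or listing.

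Proteinuria is tabulated, but the table does not show whether it is new. That matters because some subjects may have it at entry. Exclusion 201 concerns nephritis needing induction therapy, and/or cerebritis, within 1 year of screening, so older or milder renal disease is not barred by that criterion. The laboratory thresholds in exclusion 224 include a glomerular filtration rate limit but no urine protein limit.

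**Working it through.** No figure in the plan needs to be reproduced. The check sets the two analyte lists side by side and then asks what the planned counts can show.

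**Step 1. What is collected and what is analysed.**

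| Urine result | Protocol Table 12-1 | SAP Table 9-1 | Output in SAP 9.6.3 |
|---|---|---|---|
| Protein (dipstick) | Yes | Yes | n and % by category and visit |
| Blood | Yes, no condition stated | No | None |
| Protein/creatinine ratio | Reflex, if protein +1 | No | None |
| Microscopy | Reflex, if abnormal | No | None |

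Of these four, one has a planned laboratory output. The chemistry and hematology panels of Table 12-1 carry over into Table 9-1.

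**Step 2. Whether the shift table covers urine.** The SAP's shift sentence uses the general term safety laboratory values, but it sits in the chemistry and hematology paragraph and relies on CTCAE grades. Urine protein has its own paragraph and its own six-category scale. The natural reading is that no urine shift is planned. On the most generous reading the shift could extend to urine protein, because that analyte is in Table 9-1. It could not extend to urine blood, which is not.

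**Step 3. What by-visit counts can show.** Two invented examples use 5 AMG 592 subjects, the planned number in each of cohorts 1 to 3.

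- *Offsetting changes.* At baseline subject A is 2+ and B to E are Negative. At week 12 subject B is 2+ and the other four are Negative. Both visits show 4 Negative and 1 at 2+, so the table looks unchanged. A shift table would show one subject going from Negative to 2+, one from 2+ to Negative, and three unchanged.
- *Number affected.* Suppose one subject is at 2+ at each of weeks 4, 8 and 12, the urinalysis visits in SAP Appendix B. The counts are 1, 1, 1 whether this is one subject three times or three subjects once each. The number affected is anywhere from 1 to 3, and the table cannot say which.

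**Step 4. Other routes to the output.**

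- *Adverse events.* Protocol 9.2.4 requires the investigator to review results against baseline and record clinically relevant changes. Appendix 4 names urinalysis among the tests whose abnormal results count as adverse events, but only those "considered clinically significant in the medical and scientific judgment of the investigator (ie, not related to progression of underlying disease"). Recorded events are tabulated under SAP 9.6.2.
- *Disease-related events.* The pre-defined list (protocol 9.2.3.1.1.1) covers joint, skin, hair and mucosal findings and names no renal event.
- *SLEDAI-2K.* It covers the renal system, but it is exploratory and SAP 9.5.1 reports only the total score and its change. A renal item can be offset by improvement elsewhere.
- *Chemistry.* Creatinine, BUN or urea, and albumin get summaries, change from baseline, maximum and minimum, and the section's grade-shift analysis. They do not show hematuria or sediment.
- *Dose level review meetings.* They see available laboratory results, but on as-is data snapshots (SAP 7.1), not in the final analysis.

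**The case against.** The strongest reply is that the event route is an obligation and does its job. The primary endpoint concerns clinically significant changes, and the investigator must judge and record them. The carve-out for underlying disease is not a dead end: Appendix 4 requires a disease event that is worse than expected, or thought to be caused by the product, to be reported as an adverse event or serious adverse event. Events in the normal course of disease are recorded as disease-related events and tabulated. An unlisted renal finding can still qualify. This stands. A reader might infer that urine blood, sediment and the ratio never reach the primary safety output, and the documents do not support that.

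A reader might also infer that SAP 10 ("There are no changes to the protocol-specified analyses") hides a departure from the protocol. That is not supported either. Protocol 10.3.2.1 promises descriptive statistics for selected data, and 10.3.2.3.3 names no analytes, so it does not commit to every urinalysis row.

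Three further points stand. The ratio and microscopy are reflex tests, so many subjects may have no baseline value, and a summary or shift table for them would mean little. Counting every urinalysis row the SAP leaves out would exaggerate the gap, since pH, specific gravity and similar rows are not at issue. The nephritis figure in protocol 3.2.1 has no time frame and is not a risk over this study's 18 weeks.

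What the reply does not answer is that event reporting rests on case-by-case judgement, while the laboratory tables exist to show the measured values whatever that judgement was. For urine blood there is no such table, and for urine protein the table does not follow subjects from baseline.

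**Conclusion.** The point holds as a gap in presentation, not as a loss of safety reporting. Three of the four relevant urine results have no planned laboratory summary, shift table or listing. The fourth, dipstick protein, is shown in a form that cannot separate new from pre-existing proteinuria. These results reach the primary safety output only through an event that the investigator judges clinically significant and records.

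The documents give no basis for estimating how many subjects would be affected, and no such number is claimed. The conclusion rests on reading the shift sentence in SAP 9.6.3 as belonging to the chemistry and hematology paragraph. If it was meant to include urine protein, the protein part of the concern falls away, and the part about blood, ratio and microscopy remains.

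**What to change.** Make three changes to the SAP:

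1. Add urine blood to the urinalysis column of Table 9-1.
2. In 9.6.3, add a shift table from baseline to worst post-baseline value, by treatment group, for dipstick urine protein (the existing six categories) and one for urine blood (the categories the laboratory reports, which the documents do not give).
3. Add a subject listing of any reflex protein/creatinine ratio and microscopy results, with visit and treatment group. A listing is enough because these tests exist only for some subjects and visits.

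The cost is a few lines of SAP text, two small tables and one sparse listing. Urinalysis is already in the protocol schedule and already has analysis windows at weeks 4, 8 and 12 in SAP Appendix B, so no new procedure or sample is needed. This assumes that the laboratory's urine blood results and any reflex results are transferred with the rest of the panel.

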**Table 9-1. Analyte Listing**

Chemistry	Hematology	Urinalysis
Sodium	Red blood cells	Urine protein
Potassium	Antinuclear antibody	
Chloride	Hemoglobin	
Bicarbonate	Hematocrit	
Total protein	Mean corpuscular volume (MCV)	
Albumin	Mean corpuscular hemoglobin (MCH)	

Calcium	Mean corpuscular hemoglobin concentration (MCHC)	
Magnesium	Red cell distribution width (RDW)	
Phosphorus	Reticulocytes	
Glucose	Platelets	
BUN or Urea	White blood cells	
Creatinine		
Total bilirubin		
Direct bilirubin		
Alkaline Phosphatase (ALP)		
Aspartate Aminotransferase (AST) (Serum Glutamic-Oxaloacetic Transaminase (SGOT))	WBC Differential 

• Total neutrophils or segmented neutrophils

• Bands/stab

• Eosinophils

• Basophils

• Lymphocytes

• Monocytes

	
Alanine Aminotransferase (ALT) (Serum Glutamic-Pyruvic Transaminase (SGPT))		

#### **9.6.4 Vital Signs**

The analyses of vital signs will include summary statistics for baseline, post-baseline values at all time points, change from baseline to post-baseline values at all time points, post-baseline maximum/minimum and change from baseline to post-baseline maximum/minimum by treatment group for systolic blood pressure, diastolic blood pressure, heart rate and temperature.

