9.2.3.2 Vital Signs

The following measurements must be performed: systolic/diastolic blood pressure, heart rate, respiratory rate, and temperature. Subject must be in a supine position in a rested and calm state for at least 5 minutes before blood pressure assessments are conducted. If the subject is unable to be in the supine position, the subject should be in most recumbent position as possible. The position selected for a subject should be the same that is used throughout the study and documented on the vital sign CRF. The temperature location selected for a subject should be the same that is used throughout the study and documented on the vital signs CRF. Record all measurements on the vital signs CRF.

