10.3.2.3.4 Vital Signs

The analyses of vital signs will include summary statistics at selected time points by population and treatment group. Shifts in vital sign values between the baseline and the worst on-study value will be tabulated.

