### **9.6.2 Adverse Events**

The Medical Dictionary for Regulatory Activities (MedDRA) version 24.0 or later will be used to code all events categorized as adverse events, all disease-related events to a system organ class and a preferred term. The severity of each adverse event will be graded using CTCAE criteria version 4.03.

Subject incidence of all treatment-emergent, serious treatment-emergent, treatment-related, serious treatment-related, disease-related treatment-emergent, those leading to withdrawal from investigational product, and fatal adverse events will be tabulated by system organ class in alphabetical order, preferred term and grade in descending order of frequency. Subject incidence of treatment-emergent adverse events identified by

COVID-19 standardized MedDRA queries and serious adverse events occurring on or after the COVID-19 infection will also be summarized.

Subject incidence of treatment-emergent events of interest (standardized MedDRA queries and/or Amgen Medical Queries) will also be summarized according to their categories, preferred term, and worst severity grade. Events of interest could include but are not limited to Hypersensitivity, Tachyarrhythmias, Tachypnea, Hematopoietic Cytopenia, Drug Reaction with Eosinophilia, Leucocyte Changes, Infection and Infestation, Cytokine Release Syndrome, and Injection Site Reaction. Number of episodes and duration of treatment-emergent injection site reactions will be further summarized by treatment group.

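### SAP 9.6.4 has no summary of measured respiratory rate and no vital-sign shift table, and SAP 10 declares neither omission

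*SAP*

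**What the plan says.** Protocol 9.2.3.2 is explicit about what is measured: "The following measurements must be performed: systolic/diastolic blood pressure, heart rate, respiratory rate, and temperature". It also sends every measurement to the vital signs CRF.

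Protocol 10.3.2.3.4 makes two analysis commitments. The first is "The analyses of vital signs will include summary statistics at selected time points by population and treatment group". The second is "Shifts in vital sign values between the baseline and the worst on-study value will be tabulated". Neither names individual parameters, and neither leaves one out.

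SAP 9.6.4 plans baseline values, post-baseline values and changes at all time points, and post-baseline extremes with their change from baseline. It closes with "maximum/minimum by treatment group for systolic blood pressure, diastolic blood pressure, heart rate and temperature". It mentions no shift table.

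Three other places in the SAP bear on this:
- SAP 2.1 has among the primary endpoints "Clinically significant changes in physical examinations, vital signs, and laboratory safety tests".
- SAP 9.6.2 says "Events of interest could include but are not limited to Hypersensitivity, Tachyarrhythmias, Tachypnea, Hematopoietic Cytopenia", and the list goes on to cytokine release syndrome.
- SAP 10 states "There are no changes to the protocol-specified analyses".

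**The concern.** The SAP analyses fewer vital signs than the protocol collects, omits one output that the protocol planned, and says that nothing has changed. Vital-sign changes belong to the primary endpoint of a study whose stated purpose is safety. Respiratory rate is also the direct measurement behind one of the adverse-event categories that the sponsor singles out.

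At stake is the descriptive picture by treatment group. A programmer who follows SAP 9.6.4 produces tables for four parameters. If respiratory rate rose modestly with dose, and no single value was judged clinically significant, nothing in the final tables would show it. The missing shift table removes a second view, for all five parameters: how many subjects moved from baseline to an abnormal worst value.

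**Working it through.** The plan states no figure on this point, so the check is mainly a comparison of the two documents.

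**Parameters**

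| Parameter | Measured (Protocol 9.2.3.2) | Summarised (SAP 9.6.4) | Shift table planned (Protocol 10.3.2.3.4) | Shift table in SAP 9.6.4 |
|---|---|---|---|---|
| Systolic blood pressure | yes | yes | yes, as a vital sign | no |
| Diastolic blood pressure | yes | yes | yes, as a vital sign | no |
| Heart rate | yes | yes | yes, as a vital sign | no |
| Respiratory rate | yes | **no** | yes, as a vital sign | no |
| Temperature | yes | yes | yes, as a vital sign | no |

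Required set minus summarised set = {respiratory rate}. Four of five parameters are summarised and none has a shift table.

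**Is the gap closed elsewhere?** Respiratory rate is not mentioned as a measurement anywhere in the SAP. Where the SAP means a list to be open it says so, as in SAP 9.6.2 for events of interest and SAP 9.7.1.2 for pharmacodynamic assessments. SAP 9.6.4 has no such wording for its parameters. Where the SAP leaves a collected measure unsummarised on purpose, it can give the reason, as SAP 9.6.6 does for ECG. It gives none here. SAP 9.6.3 keeps the baseline-to-worst shift for laboratory values, so that output was carried over from the protocol in one section and not in the other.

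**Number of readings.** The vital-sign table in SAP Appendix B has these post-baseline rows: Days 2 to 11, 5; Days 15 to 78, 10; Days 85 to 88, 4; Days 92 to 127, 4.

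5 + 10 + 4 + 4 = 23 rows.

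With 29 planned subjects (21 on AMG 592, 8 on placebo):

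21 × 23 + 8 × 23 = 483 + 184 = 667 readings.

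Post-dose readings on Days 1 and 85 are extra. This is an upper bound: it assumes that everyone attends every visit and that enrollment is exactly as planned.

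**How well adverse-event counts would substitute.** SAP 3.2 gives a 67% chance of at least one event among 5 active subjects at a 20% event rate. This reproduces: 1 − 0.8^5 = 1 − 0.328 = 0.672. Cohorts 4 and 5 plan 3 active subjects each, and the same formula gives 1 − 0.8^3 = 1 − 0.512 = 0.488, or 49%. The 20% rate is the plan's own illustration, not an estimate for tachypnea. It shows that event counts in the smallest cohorts detect little, and that a summary of the measured values adds information.

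**The case against.** Four arguments on the other side have substance.

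1. **The protocol does not promise every parameter.** Protocol 10.3.2.3.4 names none, and Protocol 10.3.2.1 speaks of selected safety data. A SAP that picks parameters can be read as filling in detail. It does so for urinalysis: Protocol Table 12-1 lists a full panel and SAP Table 9-1 keeps urine protein only. This stands in part. A reader might infer that dropping respiratory rate flatly contradicts the protocol, but the text does not go that far. The shift table is different: Protocol 10.3.2.3.4 says it will be produced, the SAP omits it, and SAP 10 does not say so.

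2. **Clinically significant changes are still reported.** A reader might infer that a component of the primary endpoint is lost, or that reporting is left to the investigator's choice. Neither is supported. The endpoint concerns clinically significant changes. Protocol Appendix 4 makes abnormal vital signs that the investigator judges clinically significant adverse events, Protocol 9.2.3.1.1.2 makes the investigator responsible for reporting all adverse events, and SAP 9.6.2 tabulates them. Discretion lies in judging significance, not in whether to report. Tachypnea reported as an event is counted with or without a respiratory-rate summary.

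3. **Dose review is not blind to respiratory rate.** SAP 7.1 gives the dose level review meetings subject-level listings and plots of vital signs, with no four-parameter limit. A reader might infer that escalation decisions ignore respiratory rate; the documents do not say that. But Protocol 5.1 describes this review as blinded and SAP 7.1 draws it from unlocked data, so it does not replace a final comparison by treatment.

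4. **The extremes partly cover the shifts.** For the four listed parameters, SAP 9.6.4 summarises change from baseline to the post-baseline maximum and minimum. That carries some of the same information, but as group statistics rather than counts of subjects who shifted, and not for respiratory rate.

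The tachypnea link is also modest. The list in SAP 9.6.2 is illustrative and concerns coded adverse events. The mismatch would stand without it.

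**Conclusion.** The point holds as a gap in completeness and consistency. As written, the final analysis contains no by-treatment summary of one of five required vital signs, and no baseline-to-worst shift table for any of the five. Neither omission is declared. What would be missed is a group-level change in respiratory rate that stays below the threshold for an adverse event.

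The conclusion assumes that the parameter list in SAP 9.6.4 is meant to be complete and that no output outside the SAP supplies the missing tables. The count of up to 667 readings measures the data left unsummarised, not the effect on any conclusion. The study is descriptive with no formal hypothesis, and no dose rule or error rate depends on these tables. The documents do not support a claim that a respiratory safety signal would go undetected altogether. The change is still worth making: the data bear on the primary safety objective and the remedy is small.

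**What to change.** Before final lock and unblinding:

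- Add respiratory rate to the parameter list in SAP 9.6.4, with the same summaries as the other four: baseline, all post-baseline time points, change from baseline, and post-baseline maximum and minimum with their change from baseline.
- Add the baseline-to-worst shift table planned in Protocol 10.3.2.3.4 for all five parameters. Giving respiratory rate only the outputs already listed would repeat that gap. The SAP must define the shift categories and which direction counts as worst for each parameter, since the protocol section gives neither.
- If either omission is intended, declare it in SAP 10 with the reason.

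The cost is one more parameter in an existing table program, one more table, and a short definition of the shift categories. No new data, visits or design changes are needed, because the measurements are already required and recorded on the vital signs CRF.
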